11.2.2 Additional Secondary Efficacy Analyses

Additional secondary efficacy endpoints include overall complete response rate, objective response rate, subgroup analyses of CR/CRh, CR, CRh and overall complete response rates, overall survival, event-free survival, time to response, mortality rate at 30, 60, 90, and 180 days, six-month and one-year survival.

Overall complete response rate is defined as the rate of CR+CRh+CRi [CRn, CRp]+MLFS according to IWG AML response criteria (**Appendix 1**), and includes any response which achieves < 5% BM blasts by morphology.

Objective response rate is defined as the rate of CR+CRh+CRi [CRn, CRp]+MLFS+PR according to IWG AML response criteria (**Appendix 1**).

Subgroup analyses of CR/CRh, CR, CRh, and overall complete response rates will be performed by baseline disease characteristic (e.g., age group [$< 70, \ge 70$], gender, cytogenetic risk status [high, intermediate, low], prior line of therapy [1, 2, 3], TP53 gene mutations)

Overall survival (OS) is defined as the time between the date of the first dose of study drug and death from any cause. Patients who are alive or whose death status is unknown will be censored at the last date known alive on or before data cutoff date. The last known-to-be-alive date is the last non-imputed date of any subject record in the study database. This date may be the last visit date or last contact date that the subject is known to be alive.

OS (months) = (date of death or last known alive – first dose date +1) / (365.25/12)

Event-free survival (EFS) is defined as the time from the first dose of study drug until date of evidence of relapse from CR, CRh, or CRi (CRn, CRp), or death from any cause, whichever occurs first. Patients who are not known to have any of these events at study completion will be censored at the date of the last disease assessment.

EFS (months) = (date of event [relapse or death] or date of censoring – first dose date + 1) / (365.25/12)

Sensitivity analysis of OS and EFS: patients will be censored for alternative therapies or procedures such as surgery, HSCT, radiation and subsequent antileukemic therapy, etc. If a patient begins a subsequent antileukemic therapy prior to event, the patient will be censored at the date of last assessment before starting the new anti-cancer therapy. For EFS, patients with two or more consecutive missing response assessments prior to event will be censored at the last date of response assessment before the missing assessments.

Time to response (TTR) is defined as time from first dose of study drug to first CR, CRh, CRi (CRn, CRp), or MLFS and will be summarized with descriptive statistics. Time to CR/CRh and time to best overall response will be calculated.

Mortality rate is defined as rate of death from any cause within 30, 60, 90, or 180 days of first dose of study drug. Number and percentage of deaths at 30, 60, 90, or 180 days will be summarized.

Six-month survival rate is defined as the probability of survival at 6 months from first dose of study drug.

One-year survival rate is defined as the probability of survival at 1 year from first dose of study drug.

Six-month and one-year survival rates will be evaluated by KM estimate with 95% CI.

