# 8.3.2 Follow-up Period

Follow-up information will be requested by the Sponsor after end of treatment until death or withdrawal of consent, but not beyond 2 years after the last patient is enrolled. All patients will have clinical information including safety, transfusion requirements, disease and vital status information collected during the follow-up period. Depending on treatment response, patients may be required to continue follow-up at the study site for the first 6 months post treatment. After these first 6 months, follow-up can be conducted outside of study site, but follow-up information must still be provided to Sponsor as outlined.

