#### • Non-Responders:

Patients who do not respond to treatment will have bone marrow aspirate and/or biopsy performed per standard of care.

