5 STUDY POPULATIONS

Three populations will be used for analysis, the efficacy population, safety population and the evaluable population, as defined below:

- Efficacy population All patients that have been enrolled under protocol amendment 11 or later and treated with flotetuzumab at the MTD of 500 ng/kg/day as a continuous 7-day per week IV infusion during Cycle 1, have received any portion of one dose of flotetuzumab, and met the definition of PIF/ER AML based on Amendment 11 inclusion criteria . This population will be used for the primary analysis of efficacy endpoints.
- Safety population All patients who received any portion of any dose of flotetuzumab. AML and MDS will be analyzed as pooled and separate populations for safety and PK. The analysis of all safety endpoints will be based on the safety population.
- **Response evaluable population** All patients in the efficacy population that have a baseline bone marrow assessment, have at least one post-infusion assessment of their disease status or were removed from the study for reason of documented evidence of disease progression, death, or treatment-related adverse event. This population will be used in the summary of response rate as a secondary analysis.

Patients who die before having a post-infusion disease assessment will be considered evaluable for OS and EFS analyses.

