11.2 Secondary Efficacy Analyses

Counts, percentages, and two-sided exact 95% confidence intervals will be used to describe categorical secondary variables. Kaplan-Meier (KM) methods will be used to estimate time-to-event endpoints, unless otherwise specified. All secondary efficacy endpoints will be summarized in both efficacy and response evaluable population by PIF, ER, and total.

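### EFS censors living patients who never reached CR/CRh/CRi at their last disease assessment but counts their deaths whenever they occur, so the Kaplan-Meier curve is biased downward by an amount the documents do not fix

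*SAP*

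**What the plan says.** **Event.** SAP 11.2.2 measures EFS from first dose "until date of evidence of relapse from CR, CRh, or CRi (CRn, CRp), or death from any cause, whichever occurs first". Progression and treatment failure without a prior response are not events. Protocol 7.10 and 9.6.2.2 use the same definition.

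**Censoring.** For every patient without an event: "Patients who are not known to have any of these events at study completion will be censored at the date of the last disease assessment". Protocol 9.6.2.2 has the same sentence.

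**Contrast with OS.** In the same SAP section, patients alive or of unknown status are "censored at the last date known alive on or before data cutoff date".

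**Estimator.** SAP 11.2: "Kaplan-Meier (KM) methods will be used to estimate time-to-event endpoints, unless otherwise specified".

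**Deaths.** SAP 5: "Patients who die before having a post-infusion disease assessment will be considered evaluable for OS and EFS analyses". Protocol 8.3.2, where the limit counts from enrolment of the final patient: "Follow-up information will be requested by the Sponsor after end of treatment until death or withdrawal of consent, but not beyond 2 years after".

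**Assessments after treatment.** Protocol 8.3.2 says of marrow sampling: "Patients who do not respond to treatment will have bone marrow aspirate and/or biopsy performed per standard of care". Patients with MLFS are grouped with responders there and have marrows 3 and 6 months after treatment. The end-of-treatment visit is optional (Protocol 8.3.1). Non-responder follow-up data are collected every 3 months and include blood counts, progression date, further treatment and death. Neither document says whether such a contact is a disease assessment.

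**The concern.** Kaplan-Meier needs the censoring time to carry no information about the event to come. Take two patients who never respond and whose last assessment is at month 2. One dies at month 8 and stays in the denominator to month 8. The other is alive at month 12 and leaves the denominator at month 2. The only difference between them is the later outcome, and that outcome sets the censoring date.

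The usual reason for censoring at the last assessment is that relapse is seen only when someone looks for it. That reason does not reach patients who cannot relapse because they were never in CR, CRh or CRi. For them the EFS event and the OS event are the same death, yet the plan censors the two endpoints at different dates. At stake is a named secondary objective that would be reported too low, against the drug.

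**Working it through.** The plan states no EFS rate, median or event count, so there is no figure of its own to reproduce.

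**1. Direction, by hand (illustrative numbers).** Take 100 patients who never respond. Seventy die at evenly spaced times, 0.5 + k/6 months for k = 0 to 69, so the last death is at month 12. Thirty are alive beyond month 12 and were last assessed at month 2. The estimator is S(t) = Π(1 − dᵢ/nᵢ).

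- Deaths up to month 2: 10. S(2) = 90/100 = 0.90.
- The plan's rule then removes the 30 survivors, leaving 60 at risk, all of whom die by month 12.
- Deaths from month 2 to month 6: 24. S(6) = 0.90 × (60 − 24)/60 = 0.54. S(12) = 0.
- With survivors censored when last known alive: S(6) = (100 − 34)/100 = 0.66 and S(12) = 30/100 = 0.30, which are the actual event-free shares.

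**2. Level of the curve, by simulation.** From the plan: 170 patients and a cutoff at least 6 months after the last entry. Assumed: 30% reach CR/CRh/CRi; responder EFS is 1 month plus an exponential with median 8 months; non-responder survival is exponential; accrual takes 24 months; the last non-responder assessment is at the end of cycle 1 or 2. There were 1,500 runs per row.

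| Assumed non-responder median | 6-month EFS: rule / true | 12-month EFS: rule / true |
|---|---|---|
| 3 months | 35.4% / 37.1% | 14.0% / 16.0% |
| 5 months | 45.9% / 50.0% | 19.2% / 24.9% |
| 8 months | 54.0% / 61.0% | 25.0% / 36.2% |
| 12 months | 59.2% / 68.9% | 29.8% / 46.7% |

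Censoring never-responders at the last date known alive gives 12-month values of 15.8%, 24.7%, 36.1% and 46.6%, each within 0.5 points of the truth.

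**3. What moves the size.** With 25% responders, 24-month accrual and non-responder medians of 3, 4 and 6 months, the downward bias in 12-month EFS is:

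| Reading | Bias in points |
|---|---|
| Cutoff 6 months after accrual, only assessments at month 1 or 2 count | about 2, 4, 8 |
| Same cutoff, each 3-monthly contact counts as a disease assessment | 0.6 to 1.1 |
| Only assessments at month 1 or 2 count, follow-up to 24 months after accrual | 0.1, 0.3, 1.1 |

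**4. The SAP's sensitivity analyses.** One rule censors at the last assessment before two or more missed ones. If follow-up assessments are taken as due every 3 months, it also moves late deaths back to the last assessment. At a 5-month median it gives 34.9% at 6 months, against 45.9% under the main rule and a true 50.0%. The other rule censors at alternative therapy. It does not change the censoring date of a living non-responder who starts none.

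**The case against.** The strongest reply is about size.

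- **Disease assessment need not mean marrow.** Protocol 7.10 and SAP 11 assess disease by blood counts, morphology, marrow and physical examination, and Protocol 8.3.2 collects disease status at every follow-up contact. If those contacts count, the bias nearly vanishes. This stands as a limit on the size, but the documents do not settle the reading.
- **The rule applies at study completion.** Follow-up may run to 2 years after the last enrolment, and Protocol 9.8 plans an end-of-trial analysis if patients continue. This also stands. Full 2-year follow-up is not assured, however: Protocol 4.4 ends the trial on other conditions, and SAP 11.1 requires only 6 months before the data cutoff.
- **Not every patient outside CR/CRh/CRi stops being assessed at month 1 or 2.** Patients in PR may continue induction up to Cycle 6, those with MLFS have marrows after treatment, and others may have standard-of-care marrows. Lack of at least PR after 2 cycles is a listed reason for withdrawal (Protocol 5.4), but that covers only part of the group. This stands and reduces the bias further.
- **EFS carries no test or decision.** It is an additional, not a key, secondary endpoint in a single-arm trial, and OS and the mortality rates are censored properly. This stands.

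None of these points removes the mechanism or reverses its direction.

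**Conclusion.** The rule is wrong as written; the consequence is minor to moderate. For patients who never reach CR, CRh or CRi, censoring depends on later survival, so Kaplan-Meier EFS is biased downward relative to the plan's own definition. At a cutoff 6 months after accrual, with an assumed non-responder median of 3 to 6 months, the bias is about 2 to 8 points at 12 months if only assessments at month 1 or 2 count. It is about 1 point or less if 3-monthly contacts count, or with 24 months of follow-up after accrual. The direction is secure; the size is not, because every survival, response and assessment-time input is assumed.

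A reader might infer that EFS will be badly understated, for example by the 17 points (46.7% against 29.8%) in the last row of the first table. The documents do not support that. It needs a 12-month non-responder median, the early cutoff, and no assessment after month 2 in anyone outside CR/CRh/CRi. Nor does the point reach the trial's conclusion: the CR/CRh test does not use EFS.

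Different censoring dates for OS and EFS are not in themselves a fault. For patients in response, the last disease assessment is a reasonable choice.

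**What to change.** In SAP 11.2.2 and Protocol 9.6.2.2, replace the EFS censoring sentence with three statements:

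1. Patients who never reach CR, CRh or CRi and have not died are censored at the last date known alive on or before the data cutoff, as for OS.
2. Patients still in CR, CRh or CRi are censored at the last disease assessment, as now.
3. A disease assessment during follow-up is defined, saying whether a 3-monthly contact with blood counts and progression status qualifies or a marrow is required.

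The missed-assessment sensitivity rule in SAP 11.2.2 should be limited to patients in response, since it has the same fault for the others. The cost is a short text change in each document and the matching programming. Vital status is already collected for OS, so sites need do nothing new.

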#### **Disease and Vital Status**

The Sponsor will request the following clinical data that supports or gives context to the patient's reported disease status. This information is to be collected at all follow-ups for all patients.

- hematology data (i.e., CBC results per standard of care)
- applicable concomitant medications
- further treatments, including transplant status
- transfusion information date of transfusions, transfusion frequency, units, type (red blood cells, platelets), and reason for transfusion
- date of disease progression (if applicable)

• death (if applicable) - appropriately redacted documentation should be collected for source document verification (i.e. a redacted death certificate)

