11.2.1 Key Secondary Efficacy Analyses

The key secondary efficacy endpoints include CR rate, CRh rate, duration of response, postbaseline transfusion independence rate, HSCT rate and incidence and duration of hospitalization.

Duration of response (DOR) will be calculated from the time of initial documentation of response to the time of disease relapse or death due to any cause, whichever occurs first. Patients who are still in response at study completion without alternative therapies will be censored at the time of their last disease assessment.

Duration of response will be calculated for patients who achieve the first evidence of CR or CRh as primary analysis. A separate exploratory analysis will be conducted for patients who achieve the first evidence of complete response (CR, CRh, CRi [CRn, CRp], or MLFS).

DOR (months) = (date of event [disease relapse or death] or date of censoring –date of first evidence of response + 1) / (365.25/12)

Sensitivity analyses will be done for duration of response by using the additional censoring rules below:

- Censored at the date of HSCT.
- Censored at the date of other alternative therapies such as surgery, procedure, radiation and subsequent antileukemic therapy, etc.
- Patients with two or more consecutive missing response assessments prior to event will be censored at the last date of response assessment before the missing assessments.

The duration of response will be analyzed using the KM method. The 25th percentile, median and 75th percentile time (including two-sided 95% CI) will be summarized.

Post-baseline transfusion independence is defined as no transfusion during any consecutive 56-day period on-study. Post-baseline transfusion independence will be summarized for RBC and platelet transfusion separately and in total. Transfusion dependence at baseline is defined as any red blood cell or platelet transfusions during the 28 days prior to the first dose of study drug. The rate of conversion from transfusion dependence to transfusion independence will be calculated. The rate of patients who are transfusion independent at baseline and remain independent during any 56-day post-baseline period will also be calculated.

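### The OS sensitivity analysis backdates censoring to the last assessment before new antileukemic therapy, although the patient is known to be alive when that therapy starts

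*SAP*

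**What the plan says.** SAP 11.2.2 defines the main analysis first: "Overall survival (OS) is defined as the time between the date of the first dose of study drug and death from any cause". Patients not known to have died "will be censored at the last date known alive on or before data cutoff date", and that date is read broadly: "The last known-to-be-alive date is the last non-imputed date of any subject record in the study database".

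It then gives one sensitivity paragraph for OS and EFS together. The general instruction is that "patients will be censored for alternative therapies or procedures such as surgery, HSCT, radiation and subsequent antileukemic therapy, etc". The only censoring date follows: "If a patient begins a subsequent antileukemic therapy prior to event", then "the patient will be censored at the date of last assessment before starting the new anti-cancer therapy". The next sentence, on consecutive missed response assessments, is expressly limited to EFS. The dated sentence carries no such limit, so as written it governs OS too. No date is given for HSCT, surgery or radiation.

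For duration of response, the sensitivity rules in SAP 11.2.1 use the date of HSCT and the date of the therapy itself: "Censored at the date of other alternative therapies such as surgery, procedure, radiation and subsequent antileukemic therapy, etc".

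Subsequent treatment is collected. Protocol 8.3.2 (Disease and Vital Status) lists "further treatments, including transplant status" among the follow-up data requested for all patients.

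**The concern.** Relapse status is known only when someone looks, so the last assessment before new therapy is a natural place to stop EFS follow-up. Vital status is different: starting a treatment proves that the patient is alive that day. The main OS rule would credit that dated record, but the sensitivity rule does not.

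The loss is one-sided. Between the last assessment and the start of therapy, a patient who dies is counted as a death in that interval, while a patient who survives to start therapy is removed at its beginning. Such patients leave the risk set early because they survived.

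What is at stake is the purpose of the analysis. In a single-arm trial, OS is read in absolute terms, and this analysis exists to show how far later therapy shapes it. If the curve also moves because of a dating convention, a difference from main OS cannot be attributed to later therapy alone.

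**Working it through.** The plan states no OS median, event count or switching rate, so there is no OS figure to reproduce. The check has three parts.

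**1. Direction.** Compare censoring at therapy start with the SAP rule. Deaths before new therapy count under both, and deaths after it count under neither. Only the switchers' censoring times differ, and under the SAP rule they are the same or earlier. Every risk set is therefore equal or smaller with the same deaths, so each Kaplan-Meier factor, 1 − deaths/at risk, is equal or lower. This needs no distributional assumption.

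**2. Size when switching is unrelated to prognosis (assumed).** Let the death rate be λ, the switching rate μ, θ = λ + μ, and the assessment interval d. At a time s before the next assessment, the risk set under the SAP rule leaves out those who will switch before that assessment while still alive. The hazard that Kaplan-Meier estimates is then

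λ / [1 − (μ/θ)(1 − e^(−θs))].

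Integrated over one full interval, this gives a cumulative hazard of ln[(λe^(θd) + μ)/θ].

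Base case, all assumed: median OS 6 months, μ = 0.2 per month, 28-day assessments.
- λ = ln 2/6 = 0.1155; θ = 0.3155; d = 28/(365.25/12) = 0.920 months; e^(θd) = 1.3368.
- Each full interval: ln[(0.1155 × 1.3368 + 0.2)/0.3155] = 0.1163. Six intervals: 0.6976.
- Remaining 0.4805 months: ln[(λe^(θd) + μ)/(λe^(θ(d − 0.4805)) + μ)] = 0.0633.
- Total 0.7609, so 6-month OS is e^(−0.7609) = 46.7%. The true value is 50.0%, and censoring at therapy start gives 50.0%. The drop is 3.3 points.
- With 7-day assessments: 26 intervals × 0.02718 + 0.0025 = 0.7092, giving 49.2%, a drop of 0.8 points.

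Over median OS of 4 to 9 months and μ of 0.1 to 0.3 per month, the 28-day drop is about 1.4 to 5.0 points. With a further half-month gap it is about 3 to 10 points (simulation).

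A separate simulation at the planned size (170 patients, 400 replicates per scenario, administrative censoring uniform over 180 to 730 days) gave these 6-month OS values, shown as therapy-start rule → SAP rule (drop in points):

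| Median OS / median time to switch (months) | 7 days | 28 days | 91 days |
|---|---|---|---|
| 4 / 4 | 35.3 → 34.5 (0.8) | 35.3 → 32.4 (2.9) | 35.0 → 27.0 (8.0) |
| 4 / 8 | 35.5 → 35.1 (0.4) | 35.3 → 33.9 (1.4) | 35.6 → 31.5 (4.1) |
| 8 / 4 | 59.2 → 58.6 (0.6) | 59.5 → 56.9 (2.6) | 59.8 → 51.9 (7.9) |
| 8 / 8 | 59.6 → 59.2 (0.4) | 59.5 → 58.2 (1.3) | 59.5 → 55.6 (3.9) |

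The formula agrees with each drop to about 0.1 point. No replicate had a higher 6- or 12-month value under the SAP rule. In these runs later therapy has no effect on survival, so the SAP rule produces the whole drop as an apparent therapy effect.

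**3. When sicker patients switch earlier (assumed).** Take the base-case rates and multiply both by a shared gamma frailty of mean 1 and variance 0.5. True 6-month OS is (1 + 0.5 × 0.6931)^(−2) = 55.1%. The SAP rule gives about 59% and therapy-start censoring about 61%. With log-normal frailty, median OS and median time to switch both 4 months and 28-day assessments, full follow-up gives 36.2%, the SAP rule 39.5% and therapy-start censoring 42.0%. The SAP rule is still below therapy-start censoring, but both lie above the truth.

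**The case against.** The strongest reply is that switching is rarely independent of prognosis. Patients often start new antileukemic therapy because treatment has failed, and Protocol 8.3.1 itself mentions progressing patients going on to other therapy. Part 3 shows that the SAP curve can then lie above true OS, with the proposed rule further above it. This stands. A reader might infer that the rule makes survival look worse than the data support. The documents do not establish that; only the comparison with therapy-start censoring has a fixed direction.

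A reader might also infer that OS as such is biased downward. It is not. Main OS uses the last date known alive, and nothing in the sensitivity paragraph alters it. The SAP says that 6-month and 1-year survival are Kaplan-Meier estimates, but not that they will be repeated under the sensitivity rule.

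The size is also open. The SAP does not say what an assessment is for OS. Protocol Appendix 1 has blood counts about twice a week in later cycles; if such contacts count, the loss is below 1 point. Against that, Protocol 7.10 allows some even-cycle marrows to be skipped, 8.3.1 makes the End of Treatment Visit optional, and 8.3.2 sets 3-monthly follow-up for non-responders, so longer gaps are possible.

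The model lets therapy start from day 0, which censors about 16% of base-case patients at time zero. Delaying starts to day 28 reduces the base-case drop only from 3.3 to 2.8 points.

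Finally, DOR is a different endpoint, so its rule is not binding on OS. It does show that the SAP already uses therapy-date censoring, and OS depends less on assessments than DOR does.

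**Conclusion.** The point holds as a minor defect confined to the OS sensitivity analysis. The censoring date is borrowed from a disease-assessment convention and discards survival time that the main OS rule would credit. That the curve is equal to or below the one from therapy-start censoring follows from the risk sets alone.

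The size rests on assumed survival, switching and assessment spacing. At 6 months it is about 0.4 to 0.8 points with weekly assessments, about 1.3 to 5 points with 28-day assessments, and up to about 8 to 10 points with longer gaps. These figures assume exponential survival and independent switching. The net direction against true OS, or against main OS, cannot be settled from the documents, because censoring at a switch may itself be informative.

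The mortality rates and the primary CR/CRh test with its alpha are untouched, and no decision rule uses this analysis.

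**What to change.** Split the dated sentence in SAP 11.2.2 by endpoint:

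- *OS sensitivity analysis:* censor at the start date of the subsequent antileukemic therapy or the date of the procedure, naming HSCT, surgery and radiation, which now have no date. This matches the DOR sensitivity rule.
- *EFS sensitivity analysis:* keep the last assessment before the new therapy.
- Add that censoring at a change of treatment may be informative, so the OS sensitivity curve should not be read as an unbiased estimate of survival without later therapy.

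This removes the backdating artefact only; it does not make censoring at a switch non-informative. The cost is one sentence and a short caveat in the SAP, with the matching derivation in the programming plan. No new data are needed, since further treatments and transplant status are already requested in follow-up.

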# 8.3 End of Treatment Visit/Follow-up

# 8.3.1 End of Treatment Visit: 28-Days (4 Weeks) After Last Dose of Study Drug or at the Time of Treatment Failure

It is recognized that certain patients (such as those experiencing progression of disease) may be cared for in facilities other than the participating investigational site, may proceed to receive other anti-leukemic therapy, and/or may elect not to return to the investigational site. Therefore, this visit is considered optional, but should be carried out whenever possible.

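### The missed-assessment rule in the EFS sensitivity analysis can censor known deaths in patients who cannot relapse, and how often depends on a term the SAP does not define

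*SAP*

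**What the plan says.** SAP 11.2.2 runs EFS from first dose "until date of evidence of relapse from CR, CRh, or CRi (CRn, CRp), or death from any cause, whichever occurs first". Progression, non-response and treatment failure are not events. In the main analysis, only patients "not known to have any of these events at study completion will be censored at the date of the last disease assessment" are censored, so every known death counts.

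The sensitivity analysis in the same section adds two kinds of censoring:
- Alternative therapy or procedure. For subsequent antileukemic therapy, "the patient will be censored at the date of last assessment before starting the new anti-cancer therapy".
- Missed assessments, in the EFS analysis only: "For EFS, patients with two or more consecutive missing response assessments prior to event will be censored at the last date of response assessment". The date meant is that of the last assessment ahead of the gap. There is no exception for death or for patients without a remission.

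The Protocol determines how often assessments lapse. After treatment, "Patients who do not respond to treatment will have bone marrow aspirate and/or biopsy performed per standard of care" (section 8.3.2, non-responders). Of the end-of-treatment visit it says "this visit is considered optional, but should be carried out whenever possible" (section 8.3.1). Section 8.3.2 also collects vital status for all patients during follow-up, at 3-month intervals for non-responders. Neither document defines a missing response assessment.

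**The concern.** A missed-assessment rule guards against a relapse that happened unseen during the gap. That suits duration of response, where SAP 11.2.1 has the same rule and every patient is a responder. EFS covers everyone. A patient who never reached CR, CRh or CRi, including one whose best response was MLFS, has no relapse to miss.

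For such a patient the rule can only turn an observed death into a censoring at the last assessment. It can do so only if the patient lived long enough to miss two assessments. Whether a death counts then depends on how late it came. The analysis meant to test the robustness of EFS could differ from the main result because of the rule itself, not because relapse data are missing. It also sits badly with SAP section 5, which keeps patients who die before any post-infusion assessment evaluable for EFS.

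**Working it through.** The documents give no EFS rate, median or event count, so there is no stated figure to reproduce. The check is an illustration.

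**From the documents**
- 170 patients and a target CR/CRh rate of 23% (SAP 4.2). Patients below CR/CRh: 170 × 0.77 = 130.9, about 131. The CRi rate is not given.
- Marrow at the end of each 28-day cycle; lack of PR after 2 cycles is a listed withdrawal reason (Protocol 7.10, 5.4).
- At least 6 months of follow-up for the final analysis (SAP 11.1).

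**Assumed**
- Never-responder survival is exponential with median m months.
- The last marrow is at the end of Cycle 1 or Cycle 2 (0.92 or 1.84 months), half of patients each.
- All patients below CR/CRh are treated as never-responders.
- There is no subsequent therapy.

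**Step 1: hand-checkable case.** With follow-up to 24 months and spacing g between assessments, a death is removed if it falls later than the last marrow + 2g. The share of observed never-responder deaths removed is

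{½[2^(−(0.92+2g)/m) + 2^(−(1.84+2g)/m)] − 2^(−24/m)} / {1 − 2^(−24/m)}.

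For m = 5:
- Cycle grid, g = 0.92: ½(0.682 + 0.600) = 0.641; (0.641 − 0.036)/0.964 = 0.63. Deaths removed: 130.9 × 0.605 = 79.
- 3-monthly grid, g = 3: ½(0.383 + 0.337) = 0.360; (0.360 − 0.036)/0.964 = 0.34. Deaths removed: 130.9 × 0.324 = about 42.
- Only scheduled marrows can be missing: no non-responder marrow is fixed after treatment, so 0%.

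For m = 3 and m = 8 the shares are 48% and 72% on the cycle grid, and 18% and 46% on the 3-monthly grid.

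**Step 2: shorter follow-up.** The same set-up was simulated with follow-up of at least 6 months and responder median EFS of 12 months:

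| Never-responder median survival | Cycle grid: deaths removed; median EFS, main to sensitivity | 3-monthly grid: deaths removed; median EFS, main to sensitivity |
|---|---|---|
| 3 months | 55 (45%); 3.7 to 2.5 | 17 (14%); 3.7 to 3.3 |
| 4 months | 61 (53%); 4.5 to 3.0 | 24; 4.5 to 3.8 |
| 6 months | 64 (61%); 5.6 to about 4 | 30 (28%); 5.6 to 4.4 |

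**Step 3: therapy censoring.** A never-responder who starts new antileukemic therapy is already censored at the last assessment before it, usually the same marrow, so the rule then adds nothing. If a share s starts new therapy, the extra deaths removed scale by about 1 − s. The documents give no value for s.
- s = 50%: 55–64 becomes 28–32, and 17–30 becomes about 8–15.
- s = 70%: 55–64 becomes 16–19.

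**Step 4: direction.** Two effects oppose each other. Censoring at an early marrow shrinks the risk set, so the remaining early deaths weigh more and the curve drops. Removing late deaths flattens the later curve. With 35% responders and 6-month survival, cycle counting raises the median from 6.3 to 6.6 months.

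**The case against.** The strongest reply is that an assessment nobody scheduled is not missing. Non-responder marrows after treatment are left to standard of care. On treatment, the permitted skips fall only at Cycle 2 and later even cycles (Protocol 7.10), so permitted skips alone are never consecutive. On that reading the rule rarely fires. This stands as a possible reading, but the SAP does not adopt it. Nor does it remove the problem entirely: Protocol 8.3.2 schedules marrows at 3 and 6 months after treatment for MLFS patients, who cannot relapse under the EFS definition. The separate programming plan might define the term, but neither document says that it does.

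It is also fair to say that therapy censoring would remove some of these deaths anyway. That stands, and it makes the Step 2 counts upper bounds for their assumptions.

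Finally, EFS is a descriptive additional secondary endpoint. OS, the 30- to 180-day mortality rates and the six-month and one-year survival rates report late deaths without this rule. That stands too.

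A reader might infer three stronger things that the documents do not support:
- **That reported EFS is distorted.** Only the sensitivity estimate is exposed.
- **That 131 of 170 patients are affected.** That figure includes CRi patients, who can relapse, as well as early deaths and survivors who lose no event.
- **That the bias has a known sign.** It does not.

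**Conclusion.** The concern holds in limited form. As written, the rule is unsuitable for patients who never reach CR, CRh or CRi: it guards against nothing in them and can censor deaths according to how late they occur. This is more than a missing definition, because the text covers these patients without exception.

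The size cannot be fixed from the documents. It runs from near 0% of never-responder deaths if only scheduled marrows count to 14–28% or 45–61% on the two grids in Step 2. Longer complete follow-up and longer survival give more (up to 72% in Step 1), and subsequent therapy gives less. All of this rests on assumed survival, timing of the last marrow and therapy rates.

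Main EFS, OS, the OS sensitivity analysis, the primary CR/CRh test, its alpha and the sample size are untouched.

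**What to change.** Replace the missed-assessment sentence for EFS in SAP 11.2.2 with:

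> In the EFS sensitivity analysis, the missed-assessment rule applies only to patients who have achieved CR, CRh or CRi. Those who miss at least two scheduled response assessments in a row, after that response and before the event, are censored at the last response assessment preceding the gap. In patients who never achieved CR, CRh or CRi, missed assessments do not cause censoring, and death counts as an event at the date of death unless the patient was already censored for a subsequent therapy or procedure as specified above.

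The closing condition is needed. A statement that these deaths always count would override the therapy censoring in the same paragraph.

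Also state which assessments count as scheduled, on treatment and in follow-up, and whether a permitted even-cycle skip counts as missing. The cost is a few sentences in the SAP, with no new data and no effect on the primary analysis. It should be settled before the data are analysed.
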